6.12 Ancillary and Post-trial Care

Participants will be invited to participate in a follow-up study after completion of this trial.

6.13 Publication Policy

6.13.1 Trial Results

All proposed scientific publications will be discussed with the Sponsor prior to publication. Since this is an exploratory, open-label, Phase I/II trial, progress and significant findings may be presented at scientific forums/meetings and/or published during the course of the trial.

The results of the trial will be disseminated regardless of the direction of effect.

7 Ancillary Studies

There are no currently planned ancillary studies. Any future ancillary studies will be subject to separate funding and will be submitted for ethical and regulatory review as appropriate.

8 Protocol Amendments

Protocol Version and Date	Reason for Amendment
Protocol v1.0 dated 15 Jul 2017	Initial version
Protocol v2.0 dated 3 Mar 2017	relevant changes in the operational responsibilities of the study.
Protocol v3.0 dated 09 Oct 2017	Safety reporting clarification, Dose expansion clarifications
Protocol v4.0 dated 01 May 2018	To clarify the allowance of data obtained from the usual standard of care be used for screening and or baseline assessments (with consent from subjects) in order to avoid unnecessary testing of subjects and also to extend the screening/baseline window from 3 months to 6 months. Clarify that more than 1 surgeon at a site may inject vector To remove CI will confirm eligibility of all individual participants To add FST as a visual assessment Expand the number of categories for ATIMP administration surgery from related or unrelated to: unrelated, unlikely, possibly, probably or definitely

CNGB3 Gene Therapy trial for Achromatopsia

	To clarify ATIMP vector must be administered with a 1 hour window after ATIMP has thawed at room temperature.
Protocol v5.0 dated 05 Dec 2018	To increase the number of participants to be recruited in the dose expansion phase and to allow for additional doses of vector to those described to be explored.
Protocol v6.0 17 Dec 2018	Addition of wording to provide clarification regarding what is considered “safe limits”
Protocol v7.0 29 Jan 2019	Updated to remove assessments that have been reviewed and deemed to add no scientific value to continue testing, in order to reduce assessment burden to participants and clinical sites.

9 References

CNGB3 Cyclic Nucleotide-Gated Cation Channel Beta-3

DLE dose-limiting event ERG electroretinography

ETDRS Early Treatment Diabetic Retinopathy Study

eCRF electronic case report form FST Full-field Stimulus Testing

IDMC Independent Data Monitoring Committee

IVI impact of visual impairment IVI-A impact of visual impairment adult IVI-C impact of visual impairment child

MedDRA Medical Dictionary for Regulatory Activities

PA photoaversion

PCR polymerase chain reaction

QoL Quality of Life
SAE serious adverse event
SAP Statistical Analysis Plan
SD standard deviation

SD-OCT spectral domain optical coherence tomography SUSAR suspected unexpected serious adverse reaction

VA Visual Acuity

VRQoL Vision-Related Quality of Life

WHO-DD World Health Organization Drug Dictionary

1. INTRODUCTION

This Statistical Analysis Plan (SAP) specifies definitions of analysis sets, key derived variables, and statistical methods for the analysis of safety and efficacy data for the Phase I/II CNGB3 study (MGT006). This SAP is based on the protocol of study MGT006, v7.0 and replaces the original SAP dated 24 May 2019, with the key change related to the analysis of efficacy parameters as further described in Section 6.1. Titles, mock-ups and programming instructions for all statistical outputs (tables, figures, and listings) are provided in a separate document.

1.1. Trial Objectives

The primary research objective was to assess the safety of an AAV2/8 vector for hCNGB3 gene replacement in the retina based on the primary safety outcome listed in Section 2.1.

The secondary research objective was to determine whether an AAV2/8 vector for hCNGB3 gene replacement in the retina can improve retinal function, visual function and quality of life.

1.2. Trial Design

This was an open-label, non-randomized phase I/II dose-escalation trial to determine the safety and efficacy of subretinal administration of the study agent (ATIMP) in subjects with CNGB3-related achromatopsia. In the dose escalation phase, subjects were administered a single dose of ATIMP in cohorts of 3 subjects at a time (up to a maximum of 18 subjects in total). Based on toxicity data, the Independent Data Monitoring Committee (IDMC) made a recommendation on the dose to administer to the next cohort of 3 subjects.

Once an acceptable safety profile had been established in adults, up to 18 additional subjects (either children or adults), were included. The IDMC agreed to the sponsor's recommendation for the maximum tolerated dose in adults before recommending administering up to this dose in the expansion phase.

Adults were defined as subjects aged 16+ in the United Kingdom and aged 18+ in the United States.

Safety and efficacy were assessed for 6 months following the intervention by clinical examination and special investigations according to the schedule in Section 5.6 of the protocol.

Due to the rare nature of the disease, there were no formal sample size calculations performed and no formal hypothesis testing was conducted.

2. OUTCOME DEFINITIONS

2.1. Primary Safety Outcome

The primary safety outcome is defined as any of the below events occurring during the 6 weeks following administration, at least possibly related to the ATIMP, not surgery alone:

• Reduction in visual acuity by 15 Early Treatment Diabetic Retinopathy Study (ETDRS) letters or more

- Severe unresponsive inflammation (defined in Section 4.2 of the protocol)
- Infective endophthalmitis
- Ocular malignancy
- Grade III or above non-ocular suspected unexpected serious adverse reaction (SUSAR) (Protocol MGT006, Section 5.11.3.4.2 Severity or Grading of Adverse Events).

This is the same criteria as the dose limiting event in the dose escalation phase.

Overall safety will be assessed for 6 months after the intervention in this study, and a further 4.5 years in a separate long-term follow-up study (Protocol MGT007).

The adverse events preferred terms are identified in a separate file (AES_OF_INTEREST.xlsx) and saved in the ERIS system.

2.2. Efficacy Outcomes

As listed in the protocol (Section 5.6 Trial Assessments), the following efficacy outcomes will be analyzed or summarized depending on the amount of data collected:

- Visual acuity (VA)
- Contrast sensitivity
- Reading speed
- Color vision
- Static perimetry
- Full field stimulus testing (FST)
- Ocular examination
- Fundus photography
- Spectral domain optical coherence tomography (SD-OCT)
- Adaptive optics imaging
- Fundus autofluorescence
- Photoaversion (PA)
- Microperimetry
- Visual mobility
- Nystagmus
- Electroretinography (ERG)
- Quality of life (QoL) as measured by the Impact of Visual Impairment (IVI) questionnaire adult (IVI-A) and child (IVI-C) versions, and the EQ5D-5L and EQ5D-Y
- Photoaversion questionnaire.

5

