4.1.5.1 Risk of immune responses to AAV2/8-hCAR.hCNGB3

The main risk of inflammation will be during the early postoperative period after ATIMP administration, before vector capsids are degraded. The risk of inflammation during this period will be minimised by pre- and post-operative prophylactic treatment using topical and systemic corticosteroids. Persistent intraocular inflammation will be managed by topical corticosteroid therapy, with systemic corticosteroids where indicated.

The risk of inflammation is likely to be highest during the early postoperative period after ATIMP administration, before vector capsids are degraded. The risk of inflammation during this period will be minimised by pre- and post-operative prophylactic administration of topical and systemic corticosteroids. In our first clinical trial of gene therapy, intra-ocular delivery of an AAV2/2 vector was followed by transient intraocular inflammation in 3 of 12 participants. In our subsequent trial of gene therapy, intraocular administration of an AAV2/5 has been well tolerated in majority of participants to date. A minority of participants developed an episode of intraocular inflammation involving the posterior segment, which responded to further administration of systemic corticosteroids.

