5.4.2.3 Subsequent Assessments

On the first postoperative day a full clinical ocular examination will be performed. In particular, visual acuity, intraocular pressure, the degree of postoperative intraocular inflammation and the area of any residual retinal bleb will be documented. Fundus photography, autofluorescence imaging, ocular examination, intraocular pressure and SD-OCT will be performed at day 1 and each subsequent visit post ATIMP administration.

A standard post-vitreectomy treatment regimen of topical antibiotic (chloramphenicol 0.5% qds for 7 days) and steroid (dexamethasone 0.1% qds for 4 weeks) will be prescribed to minimise inflammation and protect against infection postoperatively.

Intraocular pressure of greater than 30 mmHg will be managed using appropriate ocular antihypertensive therapy.

Participants will be maintained on oral prednisolone (or other as appropriate) for 4 weeks following administration of ATIMP as described above (Section 5.4.2.2.1: Pre-operative procedure). The possible development of steroid-induced adverse effects will be monitored regularly. In particular, blood pressure will be measured and blood glucose, renal function and liver function will be evaluated through blood biochemistry at the time points specific in Table 2: Trial Assessments.

Both safety and efficacy of the ATIMP will be evaluated at various time points up to 6 months after ATIMP delivery. Evaluations will comprise primarily, ocular assessments. The nature and schedule (Section 5.6: Trial Assessments) of these is described below.

(i) Clinical assessment of intraocular inflammation

The degree of intraocular inflammation will be assessed by slit-lamp biomicroscopy at each time point. A temporary intraocular inflammatory response is expected following vitrectomy surgery. This is typically evident clinically on slit-lamp biomicroscopy as 'flare' and cells in the anterior chamber and can be of moderate (2+ cells) intensity. The degree of intraocular inflammation is expected to decline over the course of the first 4 weeks following the surgical procedure, at which time the routine topical and systemic immunosuppression will be discontinued. Prolonged or severe intraocular inflammation, or deterioration in visual acuity that may be related to intraocular inflammation, will be investigated and managed conventionally with further topical and/or systemic immunosuppression.

(ii) Evaluation of immune responses

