Up to 10 mL of blood will be sampled to measure immune response. Antibody responses to AAV capsid proteins will be investigated by ELISA at baseline and at 4 weeks, 3 months, and 6 months following ATIMP administration.

(iii) Evaluation of biodistribution

Systemic biodistribution of vector genomes will be assessed by PCR analysis of tears (a compressed cellulose sponge placed under the eye lid until swollen), saliva (a minimum of 100 µL) and serum (1 mL) at 1 day and at 4 weeks following intraocular ATIMP administration. The test will be carried out in the [REDACTED].

Gene Therapy for Achromatopsia (*CNGB3*)

(iv) Assessment of visual function and retinal imaging

Assessment of visual function and retinal imaging will be performed as outlined in Section 5.6 (Trial Assessments). They will be carried out with the same methods applied for the baseline tests (see section 8.6 for details) to allow direct comparison of the data sets. These assessments will be scheduled over a period of a day for visits at day 1, day 3, day 7, week 2, week 4 and week 6 after surgery, and up to 4 days for baseline examinations, and 3 months, 6 months following ATIMP administration. For day 1 and 3 refraction cannot reliably be measured. Therefore, the most recent refraction measurement will be used.

All participants (adults and children) will need to be able to perform reliable visual acuity testing and SD-OCT imaging, which are the principal clinical assessments both for safety and efficacy. Other clinical assessments will be undertaken as appropriate for the ability of individual participants, since there is wide variation in the abilities of individual children to perform such tests reliably; the evaluations for individuals may be restricted to those tests that they are able to perform reliably.

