3.4. Visit Windows

The following rules are applied to assign actual visits to analysis visit windows other than baseline. If a subject has two or more actual visits in 1 visit window, the visit closest to the target day will be used as the protocol visit for that visit window. The additional visit(s) will not be used in the summaries or analyses, but they can be used for determination of clinically important outcomes. If two actual visits are equidistant from the target day within a visit window, the later visit is used. All assignments will be made in chronological order. Once a visit date is assigned to a visit window, it will no longer be used for a later time point.

Table 1: Visit Windows

Visit Window Label	Time Interval	Target Day
Baseline	-6 Months - < Day 1	< Day 1
Day 1	Day 1	Day 1
Day 2	Day 2	Day 2
Day 4	Day 3 – Day 5	Day 4
Week 1	Day 6 – Day 10	Day 8
Week 2	Day 11 – Day 20	Day 15
Week 4	Day 21 – Day 36	Day 29
Week 6	Day 37 – Day 59	Day 43
Week 12	Day 60 – Day 127	Day 85
Week 24	Day 128 – Day 225	Day 169

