5.5. Other Safety Parameters

All pregnancy test data will be listed.

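### The SAP classes ocular examination as efficacy with conditional reporting, and its safety section has no summary of measured inflammation grade or intraocular pressure

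*SAP*

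**What the plan says.** **Collection.** Protocol 5.4.2.3 states: "Fundus photography, autofluorescence imaging, ocular examination, intraocular pressure and SD-OCT will be performed at day 1 and each subsequent visit post ATIMP administration". The same section has inflammation assessed at the slit lamp at each time point, and Protocol 5.4.2.1 places tonometry within the ocular examination. Table 2 of the protocol marks ocular examination at every post-dose visit. Protocol 4.1.5.1 says of timing: "The main risk of inflammation will be during the early postoperative period after ATIMP administration". For pressure, Protocol 5.4.2.3 names a level: "Intraocular pressure of greater than 30 mmHg will be managed using appropriate ocular antihypertensive therapy".

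**Classification.** SAP 2.2 includes ocular examination in the list that opens "the following efficacy outcomes will be analyzed or summarized depending on the amount of data collected".

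**Safety section.** SAP 5.1 covers the primary safety outcome and dose-limiting events, and 5.2 adverse events. SAP 5.3 covers laboratory tests, and 5.4 systemic vital signs and physical examination. The whole of SAP 5.5, on other safety parameters, reads "All pregnancy test data will be listed".

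**Visits.** SAP 3.4 keeps one visit per window, the one closest to target. Of the rest it says: "The additional visit(s) will not be used in the summaries or analyses". The sentence goes on to allow those visits to be used in determining outcomes of clinical importance, which the SAP does not define.

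**The concern.** This is a first-in-human subretinal gene therapy trial with safety as its primary objective, and Protocol 5.11.3.5.4 expects the risks to lie largely in the eye. Yet the safety section summarises measured haematology, chemistry and vital signs, and does not summarise the two routine ocular measurements that track the expected harm.

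The dose-toxicity picture for treatment-responsive inflammation, and for all pressure rises, would then rest in the safety report on what investigators chose to report as adverse events. The grades and pressures themselves would sit among the efficacy outcomes, under a reporting condition and a visit-selection rule that suit efficacy trends better than safety peaks.

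**Working it through.** No sample size, power or error-rate figure is involved. The check is a count of visits and a trace of every route by which the two measurements can enter the analyses.

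**1. Visits.** Protocol 5.4.2.3 gives "visits at day 1, day 3, day 7, week 2, week 4 and week 6 after surgery", which is 6 visits, and "3 months, 6 months following ATIMP administration", which is 2. Total 6 + 2 = 8, matching the ocular examination row of Table 2 (D1, D3, W1, W2, W4, W6, W12, W24).

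**2. Routes into SAP section 5.**

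| Route | Inflammation | Pressure |
|---|---|---|
| Primary outcome / dose-limiting event (SAP 2.1, 5.1) | Yes, severe unresponsive only | No |
| Dedicated adverse event table and listing (SAP 5.2) | Yes | No |
| General adverse event tables (SAP 5.2) | Yes, if reported | Yes, if reported |
| Summary of the measured value, by visit or peak (SAP 5.3 to 5.5) | None | None |

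**3. What the existing routes leave out.**
- *Primary outcome.* Protocol 4.2.1 requires a 3+ grade that does not fall by two steps, or to grade 0, over six weeks. An eye at 3+ that responds to treatment is not counted. Protocol 4.1.5.1 describes this kind of course in a minority of participants in an earlier AAV2/5 trial: posterior-segment inflammation that responded to further systemic corticosteroids.
- *Adverse events.* Protocol 5.11.3.5 makes an abnormal test result an adverse event when it is judged clinically significant. Severity follows CTCAE (Protocol 5.11.3.5.2), not the SUN grades that define the dose-limiting event. These tables therefore cannot show peak SUN grade by dose.
- *Pressure.* No SAP section tabulates the protocol's 30 mmHg level.

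**4. What the efficacy route gives.** SAP 6.2 plans, for each outcome by age group, dose level and time point, descriptive statistics that include the maximum, counts for categorical variables, and individual plots of treated against untreated eye. This is on the full analysis set and subject to the condition in SAP 2.2.

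**5. The visit rule applied.** Under SAP 3.4 the Week 6 window is Days 37 to 59 with target Day 43. Suppose a scheduled visit on Day 43 and an unscheduled one on Day 50. The distances from target are |43 − 43| = 0 and |50 − 43| = 7, so Day 43 is kept and the Day 50 grade or pressure leaves the summary. The Day 4 window (Days 3 to 5) works the same way: with a scheduled Day 4 visit, an unscheduled Day 5 reading is dropped. Per-visit maxima under SAP 6.2 are taken over the kept visits, so they do not recover it.

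**The case against.** The strongest reply is that the SAP already covers most of this, and much of that reply stands.

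- A reader might infer that inflammation and pressure appear in no safety analysis. The documents do not support that. Slit-lamp grades define a component of the primary safety outcome, reported by dose level with a confidence interval. Inflammation adverse events have their own table and listing. Raised pressure can be reported as an adverse event. SAP 4.7 also presents concomitant medications used for inflammation, although prophylactic steroids go to every participant, which limits what that shows.
- A reader might infer that group means would conceal a single badly affected eye. SAP 6.2 plans maxima, category counts and individual plots, so an event at a kept visit would be visible.
- A reader might take the visit rule as an absolute ban on extra visits. It is not, because the exception in the same sentence permits their use. But the exception names no outcome, and nothing ties it to inflammation grade or pressure.
- Moving to the safety set changes little. The full analysis set loses only dosed participants without a baseline or without any post-dose visit.
- Output mock-ups are in a separate document (SAP section 1), so an ocular safety table may exist there. That cannot be checked. Even so, SAP section 1 says the SAP itself specifies the methods for safety data, so the analysis should be named in it.

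What survives is narrower: the efficacy label, the conditional reporting, the absence of any measured ocular summary in section 5, and the treatment of unscheduled visits.

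**Conclusion.** The point holds in that limited form. Across eight scheduled post-dose examinations per participant, in up to 36 participants, SAP section 5 plans no summary of measured inflammation grade or pressure. Inflammation has two dedicated safety routes plus the general adverse event tables; pressure has only the general tables. A grade 3+ inflammation that responds to treatment, or a pressure spike, is left out of the measured-data summaries if it is seen at an unscheduled visit displaced by a visit closer to target. It then reaches the safety report only if reported as an adverse event.

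This rests on the SAP being followed as written, on the undefined exception in SAP 3.4 not being applied to these measurements, and on the unseen mock-ups not already containing such a table. The documents give no rate of unscheduled visits or of responsive inflammation under this product, so the number of events affected cannot be estimated. It is a worthwhile improvement to a descriptive Phase I/II plan. It does not show that ocular safety goes unanalysed.

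**What to change.** Add an ocular safety subsection to SAP section 5, on the safety analysis set and not dependent on how much data is collected. By dose level and age group, for the treated eye and for the fellow eye where measured, give:

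- the maximum post-dose grade of anterior chamber cells, flare and vitreous haze, to Week 6 and to Week 24, as counts per grade;
- the maximum post-dose intraocular pressure, and the number of eyes above 30 mmHg. That level is taken from the protocol purely as a tabulation threshold.

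State that unscheduled visits count towards these maxima, since moving the outcome to section 5 would not by itself override SAP 3.4. The per-visit summaries and plots in SAP 6.2 can stay as they are.

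The cost is SAP wording and the programming of two tables. The scheduled measurements are already required, so participants and sites carry no extra burden.

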3. ANALYSIS DEFINITIONS

3.1. Analysis Sets

For safety analyses, the safety analysis set includes all enrolled subjects who were administered ATIMP.

For efficacy analyses, the full analysis set includes all enrolled subjects who were administered ATIMP and have both a baseline and at least 1 visit after ATIMP administration.

3.2. Baseline

In general, baseline is defined as the closest visit prior to ATIMP administration and will exclude any screening observations (unless there are no other observations prior to ATIMP administration). However, for efficacy parameters with multiple planned assessments in the baseline window, the arithmetic mean will be used as the baseline value.

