4.1.5.6 Risk of adverse effects of short-term corticosteroids

Candidates will be screened for contra-indications to transient immune suppression by corticosteroids; in particular, a history of uncontrolled hypertension, diabetes mellitus, tuberculosis, renal impairment, osteoporosis, gastric ulceration, severe affective disorder and immunocompromised status. The possibility of steroid-induced adverse effects will be monitored regularly. In particular, blood pressure and blood glucose will be measured, as will renal function and liver function (at baseline, 1 day, 7 days, 2 weeks and 4 weeks after surgery).

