5.4.2.2.1 Pre-operative Procedures

For prophylaxis against potential intraocular immune responses to the ATIMP, participants will be prescribed a course of oral prednisolone, commencing at a daily dose of 0.5 mg/kg one week prior to ATIMP administration; 1mg/kg for the first week following administration, 0.5mg/kg for the second week, 0.25mg/kg for the third week and 0.125mg/kg for the fourth week.

Gene Therapy for Achromatopsia (CNGB3)

Preoperative procedures and intraocular administration of ATIMP will be as described in the Gene Therapy for Achromatopsia (CNGB3) study manual.

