5.6 Trial Assessments

Table 2: Trial assessments

	Screening	Baseline ¹			ATIMP admin	D1	D3	W1	W2	W4	W6	W12	W24
Flexibility of schedule (\pm days)		- 6 months			Day 0	\pm 0D	\pm 1D	\pm 2D	\pm 4D	\pm 7D	\pm 7D	\pm 14D	\pm 14D
Visit number	1	2	3	4	5	6	7	8	9	10	11	12	13
Informed consent	•												
Physical exam	•												
Medical history	•							•	•	•	•	•	•
Eligibility determination	•												
ATIMP administration					★								
Adverse event review		•	•	•	•	•	•	•	•	•	•	•	•
Concomitant medication review	•	•	•	•	•	•	•	•	•	•	•	•	•
Genetic screening ⁶	•												
Pregnancy test	•				•								
Vital signs ²	•	•				•		•	•	•			
Haematology		•				•		•	•	•			
Biochemistry/glucose/liver and renal function		•				•		•	•	•			
Serology		•								•		•	•
PCR						•				•			
QoL questionnaires (IVI and EQ5D-5L)		•											•
Visual acuity ³	•	•	•	•		•	•	•	•	•	•	•	•
Colour vision assessments		•	•	•								•	•
Contrast sensitivity	•	•	•	•								•	•
Reading speed		•	•	•								•	•
Static perimetry		•	•	•								•	•
Full Field Stimulus Testing		•	•	•							•	•	•
Ocular examination	•	•	•	•		•	•	•	•	•	•	•	•

CNGB3 Gene Therapy trial for Achromatopsia

	Screening	Baseline ¹			ATIMP admin	D1	D3	W1	W2	W4	W6	W12	W24
Flexibility of schedule (\pm days)		- 6 months			Day 0	\pm 0D	\pm 1D	\pm 2D	\pm 4D	\pm 7D	\pm 7D	\pm 14D	\pm 14D
Fundus photography		•				•	•	•	•	•	•	•	•
Optical coherence tomography	•	•	•	•		•	•	•	•	•	•	•	•
Adaptive optics imaging		•	•										•
Fundus autofluorescence		•	•									•	•
Pattern Electroretinography ⁴	•												•
Full field Electroretinography ⁴	•												•
Photoaversion assessments		• ⁵	• ⁵	• ⁵								•	•

¹ Baseline assessments may be performed on the same day where considered logistically and clinically appropriate

² Measurements for vital signs include: blood pressure, pulse, respiration rate, arterial oxygen saturation, temperature, height and weight

³ Visual acuity at day 1 and 3 will be assessed using the previous refraction.

⁴ ERG assessments may be performed under general anaesthesia if considered appropriate

⁵ Photoaversion Questionnaire only to be completed at one baseline visit

⁶ Not required to be repeated if previous result available from an accredited laboratory

CNGB3 Gene Therapy trial for Achromatopsia

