5.3. Clinical Laboratory Tests

Clinical laboratory tests will be displayed for the subjects included in the safety analysis set. Hematology, clinical chemistry, glucose, serology and polymerase chain reaction (PCR) laboratory tests will be presented.

Summary statistics of hematology and clinical chemistry observed values and change from baseline by parameter (unit) will be summarized by age group, dose level and overall.

All hematology and clinical chemistry values will be listed.

Serology data will be listed and summarized at each assessment by age group, dose level and overall.

All PCR values will be summarized by tissue and listed.

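### The baseline for vital signs and laboratory values can be one taken after prophylactic prednisolone has started, which would distort change from baseline as a measure of steroid effects

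*SAP*

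**What the plan says.** **Baseline rule.** SAP 3.2 states that "baseline is defined as the closest visit prior to ATIMP administration and will exclude any screening observations"; screening counts only "unless there are no other observations prior to ATIMP administration". There is one exception: "for efficacy parameters with multiple planned assessments in the baseline window, the arithmetic mean will be used as the baseline value". It covers efficacy parameters, so vital signs and laboratory values stay under the closest-visit rule. SAP Table 1 (section 3.4) gives the baseline interval as minus "6 Months - < Day 1".

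**Steroid schedule.** Protocol 5.4.2.2.1 has oral prednisolone "commencing at a daily dose of 0.5 mg/kg one week prior to ATIMP administration". The daily dose is then 1, 0.5, 0.25 and 0.125 mg/kg in weeks 1 to 4 after administration.

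**Purpose of the measurements.** On steroid effects, Protocol 4.1.5.6 says that "blood pressure and blood glucose will be measured, as will renal function and liver function (at baseline, 1 day, 7 days", and again at 2 and 4 weeks. Protocol 5.4.2.3 repeats this purpose.

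**Sampling schedule (Protocol Table 2, section 5.6).** Haematology and biochemistry have one planned pre-ATIMP sample, at visit 2, the first of three baseline visits, and none at screening. Vital signs, which include blood pressure and weight, are planned at screening and at visit 2. A footnote adds: "Baseline assessments may be performed on the same day where considered logistically and clinically appropriate".

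**Analysis.** SAP 5.3: "Summary statistics of hematology and clinical chemistry observed values and change from baseline by parameter (unit) will be summarized". SAP 5.4 likewise summarises vital signs at each time point and as change from baseline.

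**The concern.** Blood pressure, glucose, renal function and liver function are followed so that steroid effects can be seen. That needs a reference value from before the steroid. The SAP ties the reference to the ATIMP date, and the steroid starts a week earlier. No section of either document requires the baseline sample or reading to precede the first prednisolone dose.

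At stake is how the change-from-baseline columns in SAP 5.3 and 5.4 can be read. If some participants have an on-steroid reference and others do not, those columns mix two different contrasts and nothing in the output would show it. The tables are split by age group and dose level, and the escalation cohorts have three participants, so one such participant can be a third of a cell. The primary safety outcome and the dose-limiting events are not defined on these measurements, so the point does not bear on escalation decisions.

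**Working it through.** The plan states no figure to reproduce. The check sets the baseline rule against the visit schedule and the steroid schedule, then illustrates the size.

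**1. Does the baseline window overlap with steroid use?** Yes. It ends the day before Day 1 (SAP Table 1), and prednisolone begins one week before ATIMP (Protocol 5.4.2.2.1). The last 7 days of the window are on steroid.

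**2. What can the rule do, by parameter?**

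| Parameter | Planned pre-ATIMP values | How an on-steroid baseline can arise |
|---|---|---|
| Blood pressure, weight, other vital signs | Screening and visit 2 | Visit 2, or a later unscheduled reading, falls in the steroid week; the screening value is then set aside |
| Haematology, biochemistry, glucose | Visit 2 only | Visit 2 falls in the steroid week, or a later unscheduled sample does and is the closest; no planned value is discarded in favour of visit 2 |

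**3. How many participants?** The documents give no visit dates, so the share f lies anywhere from 0 to 100%. As a reference point only, assume that visit 2 is spread evenly over a six-month window of 183 days: f = 7/183 = 3.8%, or 36 × 7/183 = 1.4 of 36 participants.

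**4. How large is the distortion in an affected participant?** Assume an immediate effect proportional to daily dose, E per mg/kg/day. This is an illustration; the documents give no effect size or time course. With a pre-steroid baseline, the change at dose d is d × E. With a baseline taken on 0.5 mg/kg/day, it is (d − 0.5) × E. The mean over a group with share f affected is (d − 0.5f) × E.

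| Dose of | d | f = 0 | f = 3.8% | f = 1/3 | f = 50% | f = 100% |
|---|---|---|---|---|---|---|
| Week 1 | 1 | 1.00E | 0.98E | 0.83E | 0.75E | 0.50E |
| Week 2 | 0.5 | 0.50E | 0.48E | 0.33E | 0.25E | 0 |
| Week 3 | 0.25 | 0.25E | 0.23E | 0.08E | 0 | −0.25E |
| Week 4 | 0.125 | 0.125E | 0.106E | −0.04E | −0.125E | −0.375E |

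With one of three participants affected, the cell mean is understated by 0.167/1 = 17% at the week 1 dose and 0.167/0.5 = 33% at the week 2 dose, and its sign reverses at the week 4 dose. At f = 3.8% the week 1 mean moves by 0.5 × 0.038 = 1.9%.

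If the effect builds up slowly, a baseline taken after a few days on 0.5 mg/kg carries less than 0.5E and the distortion is smaller.

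**The case against.** The case on the other side has real force.

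- **For laboratory tests the SAP makes no choice among planned values.** With one planned sample, neither the closest-visit rule nor the screening exclusion selects anything. This stands. The laboratory risk comes from the unfixed date of visit 2 or from an unscheduled sample.
- **Nothing places visit 2 in the steroid week.** It is the first of three baseline visits, and Protocol 5.4.2.1 prefers separate days, within six months, for assessments with several baselines. The same-day footnote allows visits to be combined but does not say near surgery. This stands: an on-steroid baseline is permitted, not implied.
- **Other outputs remain.** Observed values are summarised, all haematology and chemistry values are listed, and Protocol 5.11.3.5 has clinically significant test abnormalities recorded as adverse events. This largely stands. One limit is that SAP 5.2 counts only events on or after ATIMP administration as treatment-emergent, so events that begin in the pre-operative week fall outside those tables.
- **The primary objective is the safety of the vector, and prednisolone is a non-investigational product, so the last visit before ATIMP is a reasonable reference.** This does not carry. After ATIMP the steroid dose doubles from 0.5 to 1 mg/kg and then tapers to 0.125 mg/kg. A reference taken on 0.5 mg/kg therefore isolates neither the ATIMP effect nor the steroid effect.

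A reader might also extend the point to intraocular pressure. The documents do not support that: it is measured in the ocular examination, which SAP 2.2 lists under efficacy and which has several baseline visits, so on that reading the averaging rule governs it.

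**Conclusion.** The point holds in limited form. The SAP permits an on-steroid baseline for vital signs and laboratory values. For blood pressure and weight, it can set aside a pre-steroid screening value to get there. In an affected participant, change from baseline is attenuated while the dose is high and can change sign as it tapers. The number affected is unknown (0 to 100%; about 4% under even spacing of visit 2), and the size of the distortion rests on the dose-proportional assumption.

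Three stronger readings are tempting and not supported:

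- *The rule hides steroid harm.* One descriptive contrast is distorted; observed values, laboratory listings and adverse event records remain.
- *The rule throws away pre-steroid laboratory values.* Under the planned schedule there is no second value to throw away.
- *The distortion will look like a dose, age or site effect.* That would need visit timing to differ between those groups. It is possible, but nothing in the documents shows it, and the SAP plans no formal hypothesis testing.

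The change is still worth making: the protocol gives these measurements a steroid-monitoring purpose, and the correction is nearly free.

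**What to change.** Change the SAP only; the steroid regimen and the visit schedule stay as they are. The SAP describes dosing and enrolment in the past tense, so a new scheduling rule would probably come too late. Add to SAP 3.2, in substance:

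> For haematology, biochemistry including glucose, and vital signs, baseline is the last value before the first dose of prednisolone or prednisone recorded in the eCRF. A screening vital sign is used only when no later pre-steroid value exists. Values between the first steroid dose and ATIMP administration are shown as a separate pre-dose time point. Participants with no pre-steroid value are flagged, and the age of each baseline value is shown.

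Leave intraocular pressure under its present rule.

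**Cost.** A short SAP paragraph and one derived variable. No new samples or visits are needed: Protocol 5.4.7 already has all concomitant medication, steroids included, recorded in the eCRF from consent. If nobody had an on-steroid baseline, the results stay the same and the report can say so.

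**Downsides.** Some participants may have no pre-steroid laboratory value. Screening vital signs can be old: up to 6 months before enrolment (Protocol 5.3.1.6.2) plus up to 6 months from enrolment to ATIMP (Protocol 5.3.1.6.3), or about 12 months. For weight in growing children, that would add growth to the change, which is why the age of the value should be shown. A value older than six months also lies outside the baseline interval in SAP Table 1, so the text should say whether it is allowed or the participant is flagged.
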